9.2.1 Selection of Study Population

Patients with gMG who are expected to start treatment with efgartigimod at enrolment or are within their first cycle of efgartigimod at enrolment will be eligible to enrol into the efgartigimod cohort. Patients with gMG who have not been exposed to efgartigimod and for whom it is not planned to start

treatment with efgartigimod at enrolment will be eligible to enrol into the non-efgartigimod cohort.

Physicians participating in the study will be instructed to invite all patients who meet study eligibility criteria to enrol until the enrolment period is closed.

Inclusion Criteria (efgartigimod cohort)

1. Patients diagnosed with gMG who are expected to start commercial efgartigimod at enrolment or who are within their first cycle of efgartigimod at enrolment
2. Have provided appropriate written informed consent

Inclusion Criteria (non-efgartigimod cohort)

3. Patients diagnosed with gMG who have not been exposed to efgartigimod and for whom it is not planned to start treatment with efgartigimod at enrolment
4. Have provided appropriate written informed consent

Exclusion Criteria

None

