9.3 Variables

Electronic case report forms (eCRFs) will be specifically designed for the collection of data from this study. An overview of the categories of study variables (raw data) to be collected for each enrolled patient is summarized in [Table 1](#). There may be some missing data if any assessments are not performed as part of normal clinical practice.

Table 1: Study Variables*

Category	Variables	Baseline	Follow up
Confirmation of eligibility, demographics, study status	
 Date of appropriate informed consent for study enrolment Eligibility assessment Demographic characteristics 	✓	
Past and current medical history	
 Relevant medical history including key co-morbidities (including past history of infections) 	✓	

Category	Variables	Baseline	Follow up
	
 Immune status (immunocompromised or immunocompetent) 	✓	✓
gMG Disease	
 Date of diagnosis 	✓	
	
 Criteria used for diagnosis of gMG 	✓	
	
 Antibody status (AChR, MuSK, anti-LRP4)/date 	✓	
	
 Clinical classification (Myasthenia Gravis Foundation of America recommendations) (Jaretzki, 2000) 	✓	✓
	
 Previous myasthenia crises 	✓	
	
 Thymectomy 
 Date Histology 	✓	✓
	
 MG-ADL questionnaire 	✓	✓
Renal function	
 Estimated glomerular filtration rate (eGFR) 	✓ (Most recent prior to initiation of efgartigimod therapy)	✓
gMG treatments in period from diagnosis prior to enrollment (excluding efgartigimod)	
 Drug name, start and stop dates 
 Acetylcholinesterase inhibitors Corticosteroids Other immunosuppressants (specify) Monoclonal antibodies (specify) Plasmapheresis/plasma exchange acute Plasmapheresis/plasma exchange chronic IVIg therapy acute IVIg therapy chronic Other 	✓	

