gMG treatments at or following enrollment (excluding efgartigimod)	
 Drug name, dose, start and stop dates 
 Acetylcholinesterase inhibitors Corticosteroids Other Immunosuppressants (specify) Monoclonal antibodies (specify) Plasmapheresis/plasma exchange acute Plasmapheresis/plasma exchange chronic IVIg therapy acute IVIg therapy chronic Other 	✓	✓

Category	Variables	Baseline	Follow up
Efgartigimod treatment	
 • Date of administration • Reason for interruption during cycle of treatment • Reason for permanent discontinuation whilst on study 	✓	✓
Other comedications at or following enrollment for conditions other than gMG	
 • Drug name, start and stop dates • Indication 	✓	✓
Live/attenuated vaccinations 2 months prior to enrollment to 2 months after last Vyvgart dose	
 • Live/attenuated vaccine 
 ○ Vaccine ○ Date 	✓	✓
Adverse Events (AEs)/Serious Adverse Events (SAEs)	
 • AEs, SAEs 		✓
Events of interest	See Table 2		✓

*All variables will be collected ONLY if available as part of routine clinical practice

A patient will be considered to be an efgartigimod exposed patient if he/she has received at least one dose of efgartigimod.

Additionally, taking into account the variable follow up time and time interval between cycles, the following will be measured for efgartigimod:

- Number of administrations per year
- Total duration of the exposure
- Total number of administrations

The exposure time window of efgartigimod is 56 days +/-3 days after the last dose.

Events of interest in this study will be pre-specified as per [Table 2](#) below.

Table 2: Pre-specified events of interest

Event of interest	Definition	Measurement
Serious infection	Any serious adverse event coded to the Medical Dictionary for Regulatory Activities (MedDRA) System Organ Class (SOC) of Infection and Infestation. See Section 11 for definition of Serious.	Proportion of patients who report serious infections during the course of the study in the efgartigimod treated cohort compared to the non-efgartigimod cohort. Incidence rate of serious infections per patient-years exposed in the efgartigimod treated cohort compared to the non-efgartigimod cohort.

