9.5 Study Size

A sample size of 340 patients in each of the two cohorts is proposed (680 patients in total). Recruitment will be over a 5 year period and patients will be followed for 5 years from the time the last patient is enrolled. Thus maximum follow up will be 10 years.

The estimated prevalence rate for MG is 77.7 per million persons (range 15-179) and the estimated incidence rate is 5.3 per million person-years (range 1.7–21.3).

Myasthenia gravis occurs in both genders, at all ages, and in all races. However, for sample size calculations it is proposed to use the reported serious infection prevalence in MG patients.

Statistical analysis in this study will be descriptive and exploratory, and not aimed to confirm or reject predefined hypotheses.

Sample size calculation is driven by the precision of the estimated incidence proportion of serious infection assuming similar incidence proportion to the background.

In a population-based cohort study of 3823 MG patients ([Kassardjian 2020](#)) followed for a mean of 5.4 (Standard Deviation [SD]=3.8) years, 33.4% of patients experienced a serious infection which included both emergency department visits and hospitalisation with primary diagnosis of infection. In a retrospective chart review of 358 MG patients ([Prior 2018](#)) over a 10-year period, 19% of patients experienced infection. In the argenx-sponsored ADAPT+ study final analysis with 145 efgartigimod patients followed for a mean of 1.7 years (SD=0.7), 6.2% of patients experienced at least one serious infection (serious adverse event with SOC term "Infections and Infestations").

For the current study, serious infection incidence proportion is assumed to be 20% considering varied follow-up time and definitions of serious infection in the literature and argenx-sponsored trial.

The sample size needed to achieve a 5% precision (half-width) is presented in Table 3 below with the following assumptions:

- An incidence proportion of 20% for serious infections among patients receiving efgartigimod.
- Two-sided 95% exact binomial confidence limits based on the Clopper-Pearson method.

Table 3: Precision calculations for different incidence proportions

Number of Patients	Expected Incidence Proportion	Expected Number of Patients with Event*	Lower Limit of 95% Confidence Interval (CI) of Observed Incidence Proportion	Upper Limit of 95% CI of Observed Incidence Proportion
215	15%	32	10.5%	20.5%
245	18%	44	13.4%	23.4%
264	20%	52	15.3%	25.3%

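### The efgartigimod-cohort criterion does not require patients to be efgartigimod-naive, so previously trial-exposed patients can enter as starters, and Table 1 does not say that their earlier doses must be recorded

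*Protocol*

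**What the plan says.** The numbered inclusion criterion for the efgartigimod cohort, in Section 9.2.1 and in the Section 4 abstract, reads "Patients diagnosed with gMG who are expected to start commercial efgartigimod at enrolment or who are within their first cycle of efgartigimod at enrolment". The prose in Section 9.2.1, which also appears in the abstract and Section 9.1, is worded differently: "Patients with gMG who are expected to start treatment with efgartigimod at enrolment or are within their first cycle of efgartigimod at enrolment". It leaves out the word *commercial*.

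The comparator criterion is explicit about prior exposure: "Patients diagnosed with gMG who have not been exposed to efgartigimod and for whom it is not planned to start" treatment at enrolment. Exclusion criteria are none for both cohorts. Sections 9.2 and 9.2.1 say that all eligible patients are to be invited.

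Table 1 (Section 9.3) has a row headed "gMG treatments in period from diagnosis prior to enrollment (excluding efgartigimod"). Efgartigimod has its own row, ticked for baseline and follow-up, which begins "Date of administration • Reason for interruption during cycle of treatment" and ends with the reason for permanent discontinuation. Below the table, total duration of exposure and total number of administrations are listed as derived measures.

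**The concern.** A patient coming off trial supply and starting the marketed product satisfies the numbered criterion as written. That patient is a prevalent user. Placed in the same cohort as first-time users and compared with patients who have never had the drug, such patients turn a new-user comparison into a mixed one. Matching on age, MG-ADL band and region does not correct this, because none of the three reflects prior efgartigimod.

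Two outputs are at stake. The first is the primary comparison of serious infection. Patients who continue after repeated cycles are selected for having tolerated them, which plausibly lowers their event rate. The second is anything that depends on cumulative exposure. Section 7 names long-term safety as missing information and malignancy as an important potential risk. If earlier doses are not counted, a late event is attributed to less exposure than the patient really had, which could push an apparent malignancy rate upward. The planned subgroup that stays on efgartigimod throughout (Section 9.7) could also hold a disproportionate share of these patients.

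**Working it through.** **1. The wordings applied to one case.** Take a patient who had several cycles in a trial and is about to receive marketed drug for the first time.

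| Text | Does the patient fit? |
|---|---|
| Numbered criterion, first limb (start of commercial drug) | Yes |
| Prose, first limb (start of treatment) | No, on an ordinary reading |
| Second limb, both versions (within first cycle) | No |
| Comparator criterion (never exposed) | No |
| Exclusion criteria | None to apply |

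The two versions of the same rule give different answers. A site following the numbered criterion and the instruction to invite everyone eligible would enrol this patient as a starter.

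**2. What Table 1 captures.** The pre-enrolment treatment row leaves efgartigimod out, but so does the on-study treatment row, so the exclusion only sends the drug to its own row. That row has a baseline tick and must reach back at least to the start of the first cycle for patients enrolled mid-cycle. It states no look-back limit and no source of drug. Other rows do state a window: gMG treatments go back to diagnosis, and live vaccines to two months before enrolment. The derived exposure measures have no stated starting point. Earlier trial doses are therefore neither required nor ruled out.

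**3. Size: the plan's own power figure.** Inputs from Section 9.5: comparator risk 20%, efgartigimod risk 31%, n = 270 per arm, two-sided alpha 0.05, normal approximation.

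Power = Φ[(d√n − 1.96√(2p̄(1−p̄))) / √(p₀(1−p₀) + p₁(1−p₁))]

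With d = 0.11, √270 = 16.43 and p̄ = 0.255: (1.807 − 1.208) / 0.611 = 0.98, and Φ(0.98) = 83.7%. The unpooled-variance form gives 84.0%. The stated 84% reproduces.

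**4. Size: an illustration.** Let f be the share of the efgartigimod cohort with prior exposure, and r the fraction of the 11-point excess risk that these patients still carry. Neither is in the protocol; both are assumptions. The cohort risk is then

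p₁ = 0.20 + 0.11 × [(1 − f) + f·r]

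Using the pooled formula above with n = 270:

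| f | r = 0: p₁, power | r = 0.5: p₁, power |
|---|---|---|
| 0 | 31.0%, 84% | 31.0%, 84% |
| 5% | 30.5%, 80% | 30.7%, 82% |
| 10% | 29.9%, 76% | 30.5%, 80% |
| 20% | 28.8%, 66% | 29.9%, 76% |

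**5. Where f might lie.** The only trial-exposed pool described with its follow-up in Section 9.5 is the "ADAPT+ study final analysis with 145 efgartigimod patients followed for a mean of 1.7 years". If 10% to 50% of them entered (an assumption), that is 0.10 × 145 ≈ 15 to 0.50 × 145 ≈ 73 patients, or 15/340 = 4% to 73/340 = 21% of the cohort. If all entered, it would be 145/340 = 43%. Nothing in the protocol says where in that span the true figure lies.

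**The case against.** The best defence is that the design is plainly meant to be a new-user cohort. The prose speaks of starting treatment, the second limb refers to the first cycle of the drug and not the first commercial cycle, and roll-over patients are nowhere mentioned or planned for. On this view the problem is one stray word. This stands as evidence of intent. It does not settle what sites will do, because the numbered criterion is the text they screen against.

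The pool may also be small. The protocol is dated December 2023 and already cites the ADAPT+ final analysis, while enrolment starts only after PRAC approval of the protocol. Patients already past their first commercial cycle when a site opens fit neither limb. This also stands, so 145 should not be read as an expected number.

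Analysing naive starters separately could be left to the SAP. That is true of the analysis, but eligibility and the data collected are protocol matters, and a SAP cannot separate groups that the database does not distinguish.

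Three stronger readings are tempting, and the documents do not support them:

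- *Prior exposure is absent from the database and cannot be recovered.* The efgartigimod row is ticked at baseline, so earlier doses could be entered; the fault is that nothing requires it.
- *Exposure is understated by a quarter, from 1.7/(1.7 + 5) = 25%.* The 1.7 years is follow-up, and dosing is in intermittent cycles of varying frequency, so this is not a ratio of exposures. With ten years of follow-up the same sum gives 1.7/11.7 = 15%.
- *The risk is diluted.* The protocol does not say that patients with a serious infection left ADAPT+. It reports "145 efgartigimod patients followed for a mean of 1.7 years (SD=0.7), 6.2% of patients experienced at least one serious infection", about 9 people, with no word on whether they continued. Its statement that infections did not increase with repeated cycles does not show that those who continued were at lower risk.

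**Conclusion.** The point holds as a fault in the eligibility wording with a matching gap in data specification. The numbered criterion admits previously exposed patients, the prose implies that they should not be there, only the comparator must be unexposed, and Table 1 does not ensure that earlier exposure is identified or counted.

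The size cannot be fixed from the protocol. The power figures above (76% or 80% at a 10% share, 66% or 76% at 20%) depend on an assumed share and an assumed carry-over of risk, and on that share being the same among the 270 completers. They show that a modest share could matter; they do not predict a loss. The direction is also open: plausibly lower for serious infection through selection of patients who tolerate the drug, and possibly higher for malignancy if earlier exposure goes uncounted. The change should be made because it is cheap and protects the primary comparison, and it has to be in place before enrolment.

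**What to change.** Preferred: align the numbered criterion in Section 9.2.1 and the abstract with the prose by requiring no efgartigimod exposure, in a trial or through early access, before the current first cycle. This mirrors the comparator criterion and costs one phrase.

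Alternative, if previously exposed patients are wanted for long-term safety:

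- Extend the baseline efgartigimod row of Table 1 to prior exposure: source of drug, first and last dose dates, and number of cycles.
- State that this prior exposure counts towards total duration and total number of administrations.
- Run the main cohort comparison in efgartigimod-naive starters and summarise previously exposed patients separately.

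This costs one baseline eCRF item. The downside is that a probably small number of patients leave the main comparison, so the target of 340 should then be counted in naive starters if the stated precision and power are to be kept.

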4. ABSTRACT

Title

A non-interventional, post-authorisation safety study of patients treated with efgartigimod alfa.

Rationale and Background

Myasthenia gravis (MG) is an autoimmune disease caused by immunoglobulin G (IgG) antibodies against postsynaptic antigens at the neuromuscular junction. IgG autoantibodies impair neuromuscular transmission by binding to acetylcholine receptors (AChR), muscle-specific tyrosine kinase (MuSK) or low-density lipoprotein receptor-related protein 4 (LRP4).

Myasthenia gravis can be classified into various subgroups based upon antibody status, age of onset and/or degree of muscle involvement. Ocular symptoms are the most common initial presentation of disease and about two thirds of ocular MG patients progress to generalised MG (gMG) within the first 2-3 years ([Anil 2020](#)).

Efgartigimod alfa (efgartigimod) is a human IgG1 antibody fragment engineered for increased affinity to the neonatal Fragment crystallisable Receptor (FcRn). Efgartigimod binds to FcRn, resulting in the reduction of circulating IgG including IgG autoantibodies. Efgartigimod does not affect the levels of other immunoglobulins (IgA, IgD, IgE, or IgM), or those of albumin.

In the United States (US), efgartigimod is approved for the indication of gMG in adult patients who are AChR antibody positive and in the European Union (EU) it is approved as an add-on to standard therapy for the treatment of adult patients who are AChR antibody positive.

The purpose of this study is to evaluate the important potential risks and missing information as set out in the EU Risk Management Plan (RMP) in a larger patient population for a longer duration than in clinical trials and under conditions of normal clinical practice.

Research Question and Objectives

A non-interventional 10-year Post-Authorization Safety Study (PASS) in a post-marketing setting comparing cohorts of patients with gMG treated with efgartigimod to those treated with other MG medication, in order to estimate incidence rates of serious infection and other safety events.

Primary objective

- To evaluate the overall long-term safety of efgartigimod including the occurrence of serious infections in gMG patients treated with efgartigimod compared to gMG patients not exposed to efgartigimod.

Exploratory objectives

- To evaluate the safety of efgartigimod in immunocompromised patients.
- To evaluate the safety of efgartigimod administered to patients treated with monoclonal antibodies.

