With the exception of AChE inhibitors, the complement inhibitor eculizumab, and a liquid formulation of azathioprine, which have received regulatory approval in Europe for the treatment of gMG, all other existing therapies are used off-label [Vyvgart EPAR].

In the United States (US), efgartigimod is approved for the indication of gMG in adult patients who are AChR antibody positive and in the EU it is approved as an add-on to standard therapy for the treatment of adult patients who are AChR antibody positive.

The recommended dose of efgartigimod is 10 mg/kg as a 1-hour intravenous infusion to be administered in cycles of once weekly infusions for 4 weeks. Subsequent treatment cycles are administered according to clinical evaluation. The frequency of treatment cycles may vary by patient.

In the EU Risk Management Plan (RMP) for efgartigimod, serious infections, is considered to be an important potential risk. As efgartigimod induces a transient lowering in IgG levels, there is a potential

risk for infections associated with the lowered IgG levels. In the randomized placebo-controlled study of 167 patients ARGX-113-1704, 84 patients with gMG were exposed to efgartigimod and the most frequently observed adverse reactions were upper respiratory infections (10.7% in the efgartigimod patients and 4.8% in the placebo patients) and urinary tract infections (9.5% in the efgartigimod patients and 4.8% in the placebo patients). In the patients who received efgartigimod, these events were \leq Grade 2 according to the Common Terminology Criteria for Adverse Events (CTCAE). Overall, treatment emergent infections were reported in 46.4% of patients treated with efgartigimod and 37.3% of patients treated with placebo. The frequency of infections in the efgartigimod treated patients did not increase with repeated cycles of treatment. There were no serious infections or opportunistic infections in the efgartigimod treated patients. This study will evaluate the occurrence of serious infections in gMG patients treated with efgartigimod in the real world setting under conditions of normal clinical practice compared to gMG patients who are not treated with efgartigimod.

During clinical development of the IV formulation, in the efgartigimod phase 3 placebo-controlled 26 week clinical study, ADAPT, there were 2 reported neoplasm events, 1 (1.2%) in the efgartigimod treatment arm and 1 (1.2%) in the placebo treatment arm.

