8. RESEARCH QUESTION AND OBJECTIVES

A non-interventional Post-Authorization Safety Study (PASS) in a post-marketing setting comparing cohorts of patients with gMG treated with efgartigimod to those treated with other MG medication for 10 years, in order to estimate incidence rates of serious infection and other safety events.

Primary Objective

- To evaluate the overall long-term safety of efgartigimod including the occurrence of serious infections in gMG patients treated with efgartigimod compared to gMG patients not exposed to efgartigimod.

Exploratory Objectives

- To evaluate the safety of efgartigimod in immunocompromised patients
- To evaluate the safety of efgartigimod administered to patients treated with monoclonal antibodies
- To evaluate the safety of efgartigimod in patients receiving live/attenuated vaccine
- To evaluate the safety of efgartigimod in patients with moderate to severe renal impairment

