
AEs (serious and non-serious) in patients treated with monoclonal antibodies
	
Patients receiving monoclonal antibodies other than FcRn (e.g., adalimumab, tocilizumab, ixekizumab, rituximab) within 6 months prior to efgartigimod administration.
	
Proportion of AEs/SAEs reported in patients treated with monoclonal antibodies vs patients not treated with monoclonal antibodies in the efgartigimod cohort.
 
Incidence rate of AEs/SAEs per patient-years exposed in patients treated with monoclonal antibodies vs patients not treated with monoclonal antibodies in the efgartigimod cohort.

AEs (serious and non-serious) in patients treated with live attenuated vaccine
	
Patients receiving live/attenuated vaccine (e.g., live-attenuated flu vaccine, measles, mumps and rubella, polio, smallpox, chickenpox, yellow fever, Japanese encephalitis, shingles, rotavirus) in the period of 4 weeks prior to or 2 weeks after efgartigimod administration.
	
Proportion of AEs/SAEs reported in patients who have received live/attenuated vaccine vs patients who have not received live/attenuated vaccine in the efgartigimod cohort.
 
Incidence rate of AEs/SAEs per patient-years exposed in patients who have received live/attenuated vaccine vs patients who have not received live/attenuated vaccine in the efgartigimod cohort.

AEs (serious and non-serious) in patients with moderate to severe renal impairment
	
Moderate renal impairment: eGFR 30-59 mL/min/1.73 m² Severe renal impairment: eGFR < 30 mL/min/1.73 m²
	
Proportion of AEs/SAEs reported in patients with moderate renal impairment vs patients who have normal renal function in the efgartigimod cohort.
 
Incidence rate of AEs/SAEs per patient-years exposed in patients with moderate renal impairment vs patients who have normal renal function in the efgartigimod cohort.
 
Proportion of AEs/SAEs reported in patients with severe renal impairment vs patients who have normal renal function in the efgartigimod cohort.

		Incidence rate of AEs/SAEs per patient-years exposed in patients with severe renal impairment vs patients who have normal renal function in the efgartigimod cohort.
--	--	--

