The study design includes an efgartigimod cohort and a comparator cohort of non-efgartigimod treated patients. The duration of the study is a maximum of 10 years (5 years of enrolment and 5 years of follow up). Over this time period, standard of care for the treatment of gMG is likely to evolve with the introduction of new medicinal products such as ultomiris (recently approved) and rozanolixizumab and zilucoplan (currently under review with an approval expected by end of 2023) and the potential for patients to switch treatments during this time. The comparator group, and indeed the efgartigimod group, will therefore be heterogenous in terms of treatments, thus limiting the interpretability of the results.

Furthermore, in countries where efgartigimod is marketed, it is likely that the efgartigimod cohort and the comparator cohort will differ in terms of disease severity with the more severe patients receiving efgartigimod. Thus, there will be an inherent selection bias. This could be solved by recruiting the comparator patients from countries where efgartigimod is not marketed. However, this will introduce further biases in terms of differing standards of care.

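### The comparator criterion does not match the research question, so untreated patients qualify, and it admits users of another FcRn blocker, which dilutes the serious-infection contrast

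*Protocol*

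**What the plan says.** - **Eligibility (Section 9.2.1).** The non-efgartigimod cohort takes "Patients diagnosed with gMG who have not been exposed to efgartigimod and for whom it is not planned to start treatment with efgartigimod at enrolment", plus consent. Under "Exclusion Criteria" the section lists none. Physicians are told to invite everyone who qualifies.
- **Research question (Section 8; near-identical in the opening synopsis table and Section 4).** The study is described as "comparing cohorts of patients with gMG treated with efgartigimod to those treated with other MG medication for 10 years".
- **Primary objective (Section 8).** It concerns "gMG patients treated with efgartigimod compared to gMG patients not exposed to efgartigimod".
- **Mechanism.** Section 4 states: "Efgartigimod binds to FcRn, resulting in the reduction of circulating IgG including IgG autoantibodies". Section 7 gives the reason for studying infection: "As efgartigimod induces a transient lowering in IgG levels, there is a potential" risk of infection tied to the lowered IgG.
- **Class distinction (Section 9.3, Table 2).** The monoclonal-antibody subgroup is defined as "Patients receiving monoclonal antibodies other than FcRn", so FcRn antibodies are already treated as a class of their own there.
- **Control of differences.** Matching (Section 9.1) uses age, MG-ADL band and region. The base models (Section 9.7) use treatment group and country. Imbalanced baseline confounders, or a propensity score, may be added.
- **Admitted limitation (Section 9.9).** After noting that new products will arrive and patients may switch, the protocol says: "The comparator group, and indeed the efgartigimod group, will therefore be heterogenous in terms of treatments, thus limiting the interpretability of the results".
- **Data (Section 9.3, Table 1).** gMG treatments at or after enrolment are recorded by drug name, dose, and start and stop dates.

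**The concern.** There are two separate problems in one criterion.

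1. **Treated or merely unexposed.** The research question describes a treated comparator. The objective and the criterion describe an unexposed one, which includes patients on no gMG drug. A reader of the final report could not tell which contrast was intended. If untreated patients have a lower background infection risk, they would make efgartigimod look worse.

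2. **Same mechanism in both cohorts.** The hypothesised cause of serious infection is FcRn-mediated IgG lowering. A comparator patient whose IgG is lowered by another FcRn blocker shares that hypothesised cause. If the risk is real, such patients raise the comparator rate and shrink the difference that the study is meant to show. In a safety study, a bias toward no difference deserves more caution than one toward harm.

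**Working it through.** **Setting the passages side by side**

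| Place | Comparator | Untreated patient eligible? | User of another FcRn blocker eligible? |
|---|---|---|---|
| Section 8, research question | on other MG drugs | no | yes |
| Section 8, primary objective | unexposed to efgartigimod | yes | yes |
| Section 9.2.1, criterion | unexposed, no start planned | yes | yes |

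The mismatch lies between the research question and the other two. No version keeps out another FcRn blocker. Matching does not use current treatment. Baseline adjustment cannot account for a switch made during follow-up, and no subgroup analysis listed in Section 9.7 divides the comparator by therapy.

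**Reproducing the protocol's power figure**

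Inputs from Section 9.5 and Table 4: n = 270 per arm, comparator proportion p1 = 0.20, efgartigimod proportion p2 = 0.30, two-sided alpha 0.05, normal approximation. With p the mean of p1 and p2:

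power = Φ{ [ (p2 − p1)√n − 1.96 √(2p(1 − p)) ] / √( p1(1 − p1) + p2(1 − p2) ) }

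= Φ{ [ 0.10 × 16.432 − 1.96 × 0.6124 ] / 0.6083 } = Φ(0.728) = 76.7%.

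Table 4 gives 77%. The 31% row gives 83.7% against a stated 84%. The sample-size arithmetic is sound.

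**Diluting the comparator**

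Assumption: a share f of comparators carries the full efgartigimod risk for the whole of follow-up. Then p1 = 0.20 + f × (p2 − 0.20).

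| f | p1 when p2 = 30% | Difference (points) | Power | Power when p2 = 31% |
|---|---|---|---|---|
| 0 | 20% | 10 | 77% | 84% |
| 10% | 21% | 9 | 67% | 75% |
| 20% | 22% | 8 | 56% | 64% |
| 30% | 23% | 7 | 45% | 52% |

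**Part-way switches.** Suppose 20% of comparators switch half-way through follow-up and the excess risk accrues in proportion to time. Then p1 = 0.20 + 0.20 × 0.5 × 0.10 = 21%. That is the 10% row (67%), not the 20% row (56%).

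**The opposite direction.** Suppose 20% of comparators are untreated with a 10% risk (both assumed). Then p1 = 0.8 × 0.20 + 0.2 × 0.10 = 18%. If efgartigimod's true risk is 20%, the chance of a significant difference in the direction of harm rises from 2.5% to about 8.6%.

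**The case against.** **The criterion agrees with the primary objective.** This stands. A reader might infer that eligibility contradicts the study's objective, but only the research-question sentence is out of line. Changing that sentence would resolve the mismatch as well as changing the criterion would.

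**Few untreated patients may enter, and requiring treatment may do little.** This largely stands. Matching on MG-ADL band lets a symptom-free patient in only opposite a low-scoring efgartigimod patient, and Section 9.9 expects efgartigimod to go to the more severe patients. The add-on wording is the EU indication only, and Section 9.7 foresees efgartigimod as single treatment. An acetylcholinesterase inhibitor alone would satisfy a rule of at least one gMG medication, and nothing in the documents shows that this alters infection risk.

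**The FcRn share is unknown.** This stands. The documents do not give the mechanism of the forthcoming products named in Section 9.9. The point therefore rests on the missing exclusion and on the class distinction in Table 2, not on any named drug.

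**Power is secondary here.** This stands in part. Section 9.5 calls the analysis descriptive and sizes the study on precision, with power as further support. The efgartigimod cohort's own incidence and interval are unaffected. The between-cohort contrast is nevertheless the primary objective, and Section 9.7 tests it with models.

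**The SAP can deal with it.** This is half right. Base models may be extended, and the comment on section 5 of the ENCePP checklist, where the comparator item is marked not applicable, leaves details to the SAP. Drug names and dates would allow a split at analysis. Eligibility, however, is fixed in the protocol, and the SAP can only set such patients aside after they have taken places among the 340.

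**Ending follow-up at a switch may be informative.** This stands. Such a switch is clinically driven, so this analysis should not replace the unsplit contrast.

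**Conclusion.** The point holds in two limited parts. First, the comparator is worded in two incompatible ways, so untreated patients are admitted against the research question. Second, nothing keeps users of another FcRn blocker out of the comparator, at enrolment or later, and this dilutes the contrast toward no difference if the hypothesised mechanism is right. Section 9.9 discloses heterogeneity in general but does not mention shared mechanism and sets no remedy.

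The size is illustrative only. The loss from 77% to between 67% and 45% depends on assumed shares of 10% to 30% and on equal risk throughout follow-up. It is smaller for patients who switch part-way.

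A reader might infer that the class effect would be hidden, or that the comparison could not be read at all. The documents do not support either. Masking would be near complete only if most comparators took such an agent, and nothing suggests that share. The two influences can run in opposite directions, so the net direction cannot be determined from the protocol. This is a cheap improvement to the design, not a fatal fault.

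**What to change.** 1. **Reconcile the comparator wording** across the research question (opening synopsis table, Sections 4 and 8), the primary objective and the Section 9.2.1 criterion. If a treated comparator is meant, add to the criterion that the patient receives at least one gMG medication at enrolment. If an unexposed comparator is meant, amend the research question.
2. **Define the comparator cohort** in Section 9.2.1 as not currently receiving another FcRn-blocking agent at enrolment. This defines an observational cohort and does not alter anyone's care.
3. **Pre-specify in Section 9.7 a supplementary analysis** of serious infection that splits or ends person-time at the first dose of another FcRn blocker, in either cohort. Report it beside the unsplit contrast, using the drug names and dates that Table 1 already collects.

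The cost is a slightly smaller comparator pool, less person-time in the supplementary analysis, and possibly informative censoring at the switch. The last is the reason to report both analyses. No new data are needed.
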